15.4	4	Appendix 4 – Sample Size Calculation 22			

2 List of Abbreviations and Definitions

AC	Airway Complication
AE	Adverse Event
AP	Aerosol Precaution
AR	Adverse Reaction
ASR	Annual Safety Report
CA	Competent Authority
CI	Chief Investigator
CRF	Case Report Form
CRO	Contract Research Organisation
DMC	Data Monitoring Committee
e-CRF	Electronic Case Report Form
EC	European Commission
GAfREC	Governance Arrangements for NHS Research Ethics Committees
ICF	Informed Consent Form
MA	Marketing Authorisation
MS	Member State
PI	Principle Investigator
Participant	An individual who takes part in a clinical trial
PPE	Personal Protective Equipment
QA	Quality Assurance
QC	Quality Control
SAD	Supraglottic airway device
SAE	Serious Adverse Event
SDV	Source Document Verification
SOP	Standard Operating Procedure
SSA	Site Specific Assessment
TMG	Trial Management Group
TSC	Trial Steering Committee

3 Summary/Synopsis

Title	Prevalence of airway complications and association with aerosol precautions – a prospective multicentre service evaluation
Protocol Short Title/Acronym	AeroComp
Protocol Version number and Date	v1.2 (13/10/2021)
Study Duration	5 days
Lead Site	Guy's and St. Thomas' NHS Foundation Trust
Chief Investigator	[name]
Medical condition or disease under investigation	Perioperative airway complications
Purpose of service evaluation	Identify current usage of aerosol precautions and incidence of airway complications in patients undergoing general anaesthesia.
Primary objective	Identify current rate of airway complications (defined as a composite of multiple individual components) in patients undergoing general anaesthesia for elective and emergency procedures.
Secondary objective(s)	 Risk of the primary outcome stratified by each individual component of the aerosol precaution bundle Individual complications that comprise the primary objective (airway trauma, aspiration, desaturation, difficult intubation, difficult ventilation, second intubator required, laryngospasm, failed intubation, emergency front-of-neck airway, oesophageal intubation). Association between risk of airway complications and patient COVID- 19 status.
Number of Subjects/Patients	~3600
Study Type	Service evaluation
Endpoints	 Primary Endpoint Composite outcome of perioperative airway complications Secondary Endpoints Individual airway complications Components of the aerosol precaution bundle
Main Inclusion Criteria	Adult patients undergoing general anaesthesia for relevant procedures during the pre-defined study window (as defined by this study, see Section 7) within hospitals affiliated with the Pan-London Perioperative Audit and Research Network (PLAN) and other regional trainee networks
Data collected/storage (if applicable)	Anonymised data will be stored on the PLAN REDCap secure data capture server.

4 Introduction

Although most airway management is uncomplicated, when complications occur they can be catastrophic resulting in significant morbidity and mortality [1]. The severe acute respiratory syndrome coronavirus-2 (SARS-CoV-2) pandemic has resulted in significant changes to airway management [2] due to concern over transmission of aerosolised virus particles to healthcare professionals [3]. Initial reports suggest that patients infected with SARS-CoV-2 may be more at risk of airway complications including hypoxaemia [4], airway trauma [5], and airway oedema [6]. While it is possible SARS-CoV-2 itself may be a risk factor for airway complications, aerosol precautions, designed to reduce the transmission of virus particles to healthcare workers, may also contribute. These aerosol precautions include modified anaesthetic techniques, unfamiliar equipment, and personal protective equipment (PPE).

Anaesthetic management varies, in part, depending on the patient's coronavirus disease 2019 (COVID-19) status. Personal protective equipment for droplet precautions is advised for staff dealing with COVID-19 negative patients and comprises eye protection, gloves, and surgical facemasks at the minimum [7]. COVID-19 positive or COVID-19 unknown patients require staff to use a greater level of aerosol precaution PPE, comprising respirator masks (e.g. FFP3), long-sleeved gowns, gloves and eye protection. It is currently not known whether use of aerosol precaution PPE and other methods used to reduce viral transmission during airway interventions increases the risk of airway complications, but it may be a contributing factor to difficult intubations reported in COVID-19 patients [6, 8].

We aim to describe airway management and the different components of the bundle of aerosol precautions used to protect healthcare workers, and report the associated incidence of airway complications.

5 Trial objectives and purpose

Aims

- 1. To determine the incidence of airway complications in patients undergoing general anaesthesia during the COVID-19 pandemic.
- 2. To identify components of the aerosol precaution bundle (including PPE and anaesthetic techniques) which may be associated with a greater risk of airway complications.

6 Study design & Flowchart

6.1 Study Design

AeroComp is service evaluation exploring the incidence of airway complications amongst patients undergoing general anaesthesia for surgical procedures within NHS Trusts. All adult patients undergoing any surgical procedure (with the exception of obstetric procedures) with the primary method of anaesthesia planned to be general anaesthesia will be eligible for enrolment to this study. The study duration will encompass 5 days (patients being enrolled over a 96 hour consecutive window with a further day of follow-up data collection) with an estimated total of 3600 patients being included. Individual sites are free to choose their own data collection window between 1st November

2021 and 3rd December 2021 as long as the 96 hour window commences at 07:30 on a Monday and closes at 07:29 on a Friday.

Primary outcome:

 Incidence of airway complications at both induction and emergence, defined as a composite of: airway trauma, aspiration, dental/lip/mucosal injury, change of intubation device, desaturation, three or more laryngoscopy attempts, grade 3 or 4 laryngoscopy, difficult face mask ventilation, difficult supraglottic airway device (SAD) usage, emergency front-of-neck airway, failed tracheal intubation, laryngospasm, oesophageal intubation (immediate or delayed recognition), requirement of reintubation immediately after extubation, and need for second intubator.

Secondary outcomes:

- Risk of composite outcome of airway complications will be reported for each individual component of the aerosol precaution bundle.
- Individual complications that comprise the primary outcome.
- Subjective operator assessment of airway difficulty
- Unanticipated airway difficulties necessitating significant deviation from the original airway plan.
- Composite risk of airway complication and association with confirmed/suspected COVID-19 infection, known negative COVID-19 infection without any potential COVID-19 risks, and all other patients.

7 List selection

Operating lists from all participating NHS hospitals will be included, with patients from those lists being eligible. Both elective and emergency cases will be included. The centres and local investigators will be identified by the Pan-London Perioperative Audit and Research Network (PLAN) or other national trainee research networks.

Data will be collected over a continuous 96-hour period (07:30 Monday until 07:29 Friday). For all cases, the start time of the procedure will be the time point of the first set of observations on the anaesthetic chart and used to identify those patients to include.

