10.2 Statistical analysis

Incidence of airway complications amongst the sampled population will be reported as a composite of airway complications as mentioned in **Section 9**.

Continuous data will be reported using means (standard deviation, SD) or medians (interquartile ranges [range]) where appropriate. Categorical data will be reported as numbers (percentages, %) with 95% confidence intervals (CI) calculated using an appropriate method, where applicable. A p value of < 0.05 will be considered as statistically significant. Relationships between categorical variables and outcome measures will be presented as univariate odds ratios with accompanying p-values (Pearson's Chi-square test with Yates' continuity correction). Univariable logistic regression models will be fitted to investigate potential associations between variables describing patient, operator or procedural characteristics and the primary outcome of incidence of airway complications. A multivariable logistic regression model will then be fitted to include all covariates to obtain adjusted association estimates. Variables included in the regression modelling will be selected based on scientific and clinical plausibility of affecting the outcome of airway management.

11 Ethical considerations

This study is designed as a service evaluation, and no ethical approval is expected to be required. As we are collecting routinely captured data with no patient identifiable data, and will not involve either direct patient contact or influence their care in any way, no patient consent will be required. Approval from the Caldicott Guardian at the lead site (Guy's and St. Thomas' NHS Foundation Trust, London, UK), and audit registration at all recruiting centres will be required prior to commencing the project. Participating hospitals will ensure that their local investigators will be appropriately trained, but no GCP certification will be required from investigating teams as this is a service evaluation. The local PI will ensure that no patient identifiable information will be stored during the study.

12 Financing and Insurance

No funding will be required for this study. All investigators will be NHS employees working in their respective trusts and standard NHS Indemnity will apply.

13 Reporting and dissemination

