- 6) Second airway manager: if a second individual took over management of the airway following management by the initial airway manager their grade should be recorded here and "second airway manager required" ticked within the complication section. Leave blank if not applicable.
- 7) Other: this applies to, for example, rigid bronchoscopes, jet ventilators and transnasal humidified rapid-insufflation ventilatory exchange. This should be ticked only if it was the primary airway device following induction of anaesthesia. Typically this will be a planned technique involving pre- +/- per-oxygenation following discussion with the operating surgeon beforehand. Also select if the primary means of oxygenation during the procedure is via a surgically placed jet ventilator (e.g. laryngeal procedures) and no other airway device is placed prior or subsequently by the anaesthetist. The exact device used does not have to be specified.
- 8) Tracheal intubation attempts/laryngoscopy grade should be left blank if intubation is not attempted. The grade here refers to the Cormack and Lehane system as modified by Yentis and Lee, shown below.
- 9) If the patient was not woken up at the end of surgery, emergence complications should not be recorded. If the patient was woken up and then immediately reintubated, this should be recorded as: Woken up: Yes; Reintubation immediately post-procedure: On emergence.
- 10) Only death due to hypoxia or another complication of airway management should be recorded.
- 11) Recognised oesophageal intubation is detected after the first but before the fourth ventilatory breath has been delivered. Delayed recognition is when four or more ventilatory breaths have been delivered.

	1	2		3	
Original Cormack and Lehane system	Full view of the glottis	Partial view of the glottis or arytenoids		Only epiglottis visible	Neither glottis nor epiglottis visible
View at laryngoscopy	E	Y	Y		
Modified system	1 As for original Cormack and Lehane above	2a Partial view of the glottis	2b Arytenoids or posterior part of the vocal cords only just visible	3 As for original Cormack and Lehane above	4 As for original Cormack and Lehane above

E = epiglottis, LI = laryngeal inlet. From Yentis SM, Lee DJH. (1998) Grading of direct laryngoscopy. Anesthesia. 53:1041-4.

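### Airway techniques that act only at induction are analysed against a composite that also counts emergence events, which can pull their odds ratios towards 1

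*Protocol*

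**What the plan says.** Section 6.1 defines the primary outcome across both phases: "Incidence of airway complications at both induction and emergence, defined as a composite of" a list that runs from airway trauma to the need for a second intubator. Section 10.2 gives its denominator: "Incidence of airway complications amongst the sampled population will be reported as a composite of airway complications as mentioned in" Section 9.

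The association analyses use the same outcome:

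- 6.1, secondary outcomes: "Risk of composite outcome of airway complications will be reported for each individual component of the aerosol precaution bundle".
- 10.2, on the logistic models: they investigate "potential associations between variables describing patient, operator or procedural characteristics and the primary outcome of incidence of airway complications".

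Aim 2 in section 5 counts anaesthetic techniques as well as PPE among the bundle components. Section 9.1 and the case record form (CRF, Appendix 2) record pre-oxygenation, mask ventilation after induction, direct or video laryngoscopy, and cricoid force.

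The CRF has separate induction and emergence columns for the complications and asks whether the patient was woken. Note 9 says: "If the patient was not woken up at the end of surgery, emergence complications should not be recorded". Note 8 says: "Tracheal intubation attempts/laryngoscopy grade should be left blank if intubation is not attempted". Neither distinction is carried into the outcome used for the association analyses.

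**The concern.** A technique applied and finished at induction can show its effect in induction events. If emergence events do not depend on it, they add the same background risk to exposed and unexposed patients and move the odds ratio towards 1. Aim 2 is one of only two aims, and section 13 intends the results to inform practice. A diluted estimate could lead readers to regard a technique as harmless when the induction data alone would have shown an association.

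A second mechanism can work the other way. Some composite items can occur only if intubation is attempted. If a technique is used more often in intubated patients, it inherits their extra risk in a crude analysis. Section 10.2 plans a multivariable model with covariates chosen for plausibility, but it does not name airway device or attempted intubation.

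**Working it through.** **1. The plan's own figure.** Appendix 4 takes N = 1,000,000, p = 0.05, d = 0.01, design effect 1 and Z = 1.96:

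n = N·p(1−p) / [(d²/Z²)(N−1) + p(1−p)] = 47,500 / (26.03 + 0.0475) = 1821.4, so 1822.

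This reproduces. It concerns the all-patient composite incidence, which this point leaves as it is. The expected sample is 50 × 18 × 4 = 3600.

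**2. Dilution of an induction odds ratio.** The composite risk in the unexposed is 5% (section 10.1). The share s of that risk arising at emergence is assumed. Emergence events are taken as independent of induction events and unaffected by the technique.

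- Emergence risk: e = 0.05·s
- Induction risk, unexposed: p0 = 1 − 0.95/(1 − e)
- Induction odds, exposed: o1 = OR·p0/(1 − p0)
- Composite risk, exposed: c1 = 1 − (1 − e)/(1 + o1)
- Composite odds ratio: [c1/(1 − c1)] / (0.05/0.95)

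Worked case, s = 0.3 and OR = 2.0: e = 0.015; p0 = 1 − 0.95/0.985 = 0.0355, odds 0.0368; o1 = 0.0737; c1 = 1 − 0.985/1.0737 = 0.0826, odds 0.0900. The ratio is 0.0900/0.0526 = 1.71.

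| Emergence share (assumed) | True induction OR 2.0 reads as | True induction OR 1.5 reads as |
|---|---|---|
| 10% | 1.90 | 1.45 |
| 20% | 1.81 | 1.40 |
| 30% | 1.71 | 1.36 |
| 50% | 1.51 | 1.26 |

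**3. Does losing events cost more than dilution?** Take 3600 patients, 20% exposed (assumption: 720 against 2880), two-sided 5% level, normal approximation without continuity correction or clustering. With a true odds ratio of 1.5 and a 30% emergence share, power is about 55% on induction events alone and 43% on the composite. With an odds ratio of 2.0 it is 95% and 89%. Under these assumptions the narrower outcome has more power despite fewer events.

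**4. Bias upwards from device choice.** All inputs are assumed: a 3% risk common to everyone, a further 4% intubation-only risk, and a technique with no effect used in 30% of intubated and 5% of other patients. The risk in intubated patients is 1 − 0.97 × 0.96 = 6.88%. With half of patients intubated:

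- Exposed: (0.15 × 0.0688 + 0.025 × 0.03)/0.175 = 6.33%
- Unexposed: (0.35 × 0.0688 + 0.475 × 0.03)/0.825 = 4.65%
- Crude odds ratio: 1.39

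At 60% and 70% intubated it is 1.31 and 1.23. If the technique is equally common in both groups, it is 1.00.

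**The case against.** The strongest reply is that the pooled odds ratio answers a legitimate question: the overall risk per anaesthetic. Section 6.1 chose that question on purpose. This stands for aim 1 and for PPE, which may matter at both phases. It does not settle the matter for techniques confined to induction, where a phase-specific result is the more informative one.

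The dilution is also conditional. Trauma or desaturation at emergence could follow from what was done at induction, and then emergence events are not pure background. Many listed items arise while the airway is being secured, so the emergence share may be small; at 10% the loss is only from 2.0 to 1.90. Both points limit the size. In addition, adjusting for device conditions on a choice that may itself be part of the precautions, so the adjusted result answers a narrower question and should be labelled so.

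A reader might infer more than the protocol supports:

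- **Individual complication rates are understated.** Section 6.1 lists "Individual complications that comprise the primary outcome" without a denominator, and the sampled-population sentence in 10.2 governs only the composite. A statistical analysis plan can settle this.
- **Hospitals become non-comparable.** No comparison between hospitals is planned.
- **Many patients were never at risk.** The protocol gives no share woken or intubated, and section 7.2 excludes patients who already have an airway device in place.
- **Patients managed with a supraglottic device cannot have intubation events.** Section 9.1 and the CRF include failed intubation followed by continuing on such a device. The criterion is attempted intubation, not the device finally used.

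**Conclusion.** The point holds for one part of the plan: the associations of induction-only techniques under aim 2. Sections 6.1 and 10.2 fix the pooled composite as their outcome, so this is a stated choice and not a detail left open. If emergence events are unrelated to the technique, a true induction odds ratio of 2.0 reads as about 1.5 to 1.9 over emergence shares of 50% down to 10%. The direction follows from that independence assumption; the size depends on a share that the protocol does not give. Dilution is not the only possible bias, because uneven technique use between intubated and other patients can raise a crude odds ratio. The primary incidence, its all-patient denominator and the sample size of 1822 are unaffected.

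**What to change.** 1. Keep the all-patient pooled composite for the headline incidence and for the PPE associations.
2. In 10.2, name the techniques regarded as acting only at induction and analyse them against an induction-phase composite. Tracheal intubation attempts and laryngoscopy grade carry no phase on the CRF, so the text should assign them to induction; reintubation belongs to emergence.
3. Fit these models within attempted-intubation or airway-device group, or adjust for it. A blank attempts field can mean either not attempted or missing. The not-attempted option on the subjective-ease item for tracheal intubation helps to separate the two.
4. Report the emergence composite separately among patients with woken up = yes.

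No new data are needed: phase, waking, device and attempts are already on the CRF. The cost is some wording in 10.2, a few extra table columns, and fewer events in the phase-specific models, which limits how many covariates they can carry.

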Additionally, the lead for each site will submit, via the on-line REDCap system, the study week that site has selected (from one of weeks commencing 1st, 8th, 15th, 22nd or 29th November), the total number of eligible procedures for each 24 hour period of the study, and the list of all local investigators involved in the study (to enable production of certificates to demonstrate involvement as well as to allow naming of all collaborators on any manuscripts arising from the study). The site details data capture form is provided in *Appendix 3*.

All investigators and any other individuals contributing to the study will be required to comply with the Data Protection Act 2018 and the NHS code of confidentiality.

Data to be collected:

- Site (automatically populated dependent upon the login credentials of the local investigator)
- Day of the study
- Age of patient (grouped into 18-39, 40-59, 60-79 and \geq 80 years)
- Sex of patient
- American Society of Anesthesiologists (ASA) physical status
- Patient body mass index (BMI), grouped into underweight (< 18.5 kg/m²), normal (18.5 24.9 kg/m²), overweight (25.0 29.9 kg/m²), class 1 obesity (30.0 34.9 kg/m²), class 2 obesity (35.0 39.9 kg/m²), class 3 obesity (>= 40.0 kg/m²)
- Surgical urgency (elective; expedited; urgent; emergency)
- Start time of procedure (first set of observations entered into the anaesthetic record), grouped into daytime (07:30–17:59); evening (18:00–23:59); and overnight (00:00–07:29)
- Surgical specialty
- Surgical severity (minor; intermediate; major)
- Location of procedure: within or outside the main operating theatre complex (including stand-alone day surgery units), used to identify "remote-site anaesthesia".
- Grade of anaesthetist managing airway (initial airway manager and second airway manager if required)
- PPE worn by anaesthetist managing airway:
 - Eye protection: visor; goggles; other

- Respiratory protection: surgical mask; disposable FFP2/3 mask; re-usable FFP2/3 mask; powered air-purifying respirator; other

- Body protection: plastic apron; long-sleeved gown; hazmat suit; other
- Gloves: single pair; double pair; other
- Airway management technique- pre-oxygenation, mask ventilation, apnoeic oxygenation
- Airway equipment utilised to maintain oxygenation and facilitate anaesthesia, divided into:

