 - Airway devices utilised: facemask, supraglottic airway device; tracheal tube; other (including rigid bronchoscope, jet ventilator and transnasal humidified rapid-insufflation ventilatory exchange)
 - Airway techniques including: direct laryngoscopy; videolaryngoscopy; use of a flexible bronchoscope over which a tracheal tube is passed, categorised into whether performed awake or asleep
 - Use of cricoid force?

- Adjunct equipment including: bougie; stylet; Oxford or HELP pillow; high and lowflow nasal cannulae; aerosol boxes or drapes; as well as a free text option for other potential equipment

- Patient COVID-19 status:
 - Positive: RT-PCR or lateral flow test positive for SARS-CoV-2; OR symptoms consistent with COVID-19 with no SARS-CoV-2 test available; OR recent exposure to SARS-CoV-2
 - Negative: RT-PCR or lateral flow test negative for SARS-CoV-2 infection; AND actively cohorted with other COVID-19 negative patients for the entirety of their hospital stay prior to this operation; AND self-isolated according to institutional guidelines.
 - Unclear: No SARS-CoV-2 result available with no risk factors; OR not self-isolated according to institutional guidelines; OR not in a COVID-19-free pathway.
- Whether anaesthesia was terminated at the end of the procedure with a plan to wake up the patient (emergence from anaesthesia).

Airway complications:

- Number of tracheal intubation attempts.
 An attempt is defined by the number of times the laryngoscopy device is inserted or reinserted into the patient's airway.
- Best grade of laryngoscopy: modified Cormack and Lehane grading [9] into 1, 2a, 2b, 3 and 4.
- The following complications categorised into induction and emergence (defined as the period around the time of cessation of anaesthesia until hand over of patient to recovery/intensive care staff):
 - Airway trauma: evidence of airway bleeding or oedema.
 - Dental injury (arising solely from anaesthetic, rather than surgical, interventions)
 - Lip and mucosal injuries (arising solely from anaesthetic, rather than surgical, interventions)
 - Pulmonary aspiration: inhalation of oropharyngeal or gastric contents into the larynx and lower respiratory tract [10]
 - Change of intubation device: use of an additional airway device, e.g. change from supraglottic airway to tracheal tube, change from direct to videolaryngoscopy (or vice versa), use of bougie if not initially anticipated, change in type of laryngoscope e.g. McCoy vs Macintosh blade

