 - Desaturation: reduction in oxygen saturations to ≤90% during airway management
 - Severe Desaturation: reduction in oxygen saturations to ≤80% during airway management
 - Difficult mask ventilation: need for two-person (or more) mask ventilation
 - Difficult SAD insertion: multiple insertion attempts; excessive leak; insufficient ventilation; change of SAD size/design

- Failed tracheal intubation even after intervention of a second airway manager, including:

- If oxygenation and provision of anaesthesia was possible via SAD and a decision was made to continue with surgery

- If a decision was made to wake the patient and abandon surgery
- If this resulted in death this should be recorded separately, as above
- Laryngospasm: unwanted muscular response of the larynx that produces partial or complete obstruction of the laryngeal airway [11].
- Oesophageal intubation (recognised): tracheal tube placed in the oesophagus and recognised before delivery of the fourth ventilatory breath
- Oesophageal intubation (delayed recognition): tracheal tube placed in the oesophagus and 4 or more ventilatory breaths delivered.
- Reintubation within 30 minutes of the end of the procedure
- Second airway manager: initial airway manager either requests the assistance of a second individual to directly manage the airway or the supervising anaesthetist requests a second individual to take over management of the airway.
- Emergency front-of-neck airway
- Death due to hypoxia or other complication of airway management.
- Significant deviation from original airway plan
- Subjective assessment of ease of 1) mask ventilation, 2) SAD placement and use, and
 3) tracheal intubation, using a 5-point Likert scale (1-5) with addition of "not attempted" for each question

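### No pre-induction judgement of airway difficulty is collected, so adjusted associations for airway techniques and equipment may be confounded by indication

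*Protocol*

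**What the plan says.** Aim 2 (Protocol Section 5) is "To identify components of the aerosol precaution bundle (including PPE and anaesthetic techniques) which may be associated with a greater risk of airway complications". The first secondary outcome in Section 6.1 follows from it: "Risk of composite outcome of airway complications will be reported for each individual component of the aerosol precaution bundle". The Introduction (Section 4) counts changed anaesthetic technique and unfamiliar equipment among the aerosol precautions, alongside PPE.

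Section 9.1 collects the technique exposures, among them "Airway techniques including: direct laryngoscopy; videolaryngoscopy; use of a flexible bronchoscope over which a tracheal tube is passed", and adjuncts such as bougie and stylet. The patient and procedure variables are age band, sex, ASA status, BMI band ("Patient body mass index (BMI), grouped into underweight" through to class 3 obesity), urgency, start time, specialty, severity, location, operator grade and COVID-19 status. The CRF adds whether induction was rapid-sequence.

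Section 10.2 plans univariable models, then a multivariable logistic model that gives adjusted association estimates. On covariates it says: "Variables included in the regression modelling will be selected based on scientific and clinical plausibility of affecting the outcome of airway management".

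Three items come close to expected difficulty:
- the secondary outcome "Unanticipated airway difficulties necessitating significant deviation from the original airway plan" (Section 6.1);
- the item recorded for it, "Significant deviation from original airway plan" (Section 9.1);
- the 5-point ratings, "Subjective assessment of ease of 1) mask ventilation, 2) SAD placement and use, and" tracheal intubation (Section 9.1).

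Neither Section 9.1 nor the legible part of the CRF contains a pre-induction airway assessment, a history of difficult airway, or a yes/no item on expected difficulty.

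**The concern.** An anaesthetist who expects a difficult airway may choose a different laryngoscope, adjunct or approach from the start. The same expectation plausibly predicts the composite, which includes poor laryngoscopic view, repeated attempts, difficult mask ventilation and the need for a second operator. Expected difficulty is then a common cause of exposure and outcome, and so meets the Protocol's own criterion for a covariate. A plausibility rule can only choose among variables that were collected, and no analysis plan can supply one that was not.

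At stake is the reading of Aim 2 for technique and equipment. An adjusted odds ratio above 1 for such a component could reflect the patients in whom it was chosen. Equally, a real benefit could be hidden.

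**Working it through.** **Protocol figures.** Appendix 4 gives n = N·p(1−p) / [(d²/z²)(N−1) + p(1−p)] with N = 1,000,000, p = 0.05, d = 0.01, z = 1.96 and design effect 1. That is 47,500 / (26.03 + 0.0475) = 1821.4, rounded up to 1822, as stated. The expected recruitment also reproduces: 50 centres × 18 a day × 4 days = 3600. Neither figure is in dispute. Both concern the precision of the incidence, which this point does not touch.

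**Can a collected item stand in for expected difficulty?**

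| Item | Why it does not fully serve |
|---|---|
| Laryngoscopy grade, number of attempts, second operator | They feed the composite, so adjusting for them conditions on the outcome |
| Ease ratings | They have a not-attempted option, so they describe what happened; they are also a secondary outcome |
| Deviation from plan | A result of airway management, and itself a secondary outcome |
| BMI, ASA, specialty, urgency, operator grade | Baseline, but only partial proxies |
| Awake or asleep technique | Partial proxy, and also part of the exposure |

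**Size of crude confounding.** The Protocol gives no inputs, so all of these are assumed: expected difficulty in p0 = 5% of patients not given the technique and in p1 = 10% or 20% of those given it, a 3- to 5-fold risk (R) with expected difficulty, and no true technique effect. The spurious risk ratio is

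[1 + p1(R − 1)] / [1 + p0(R − 1)]

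- p1 = 10%, R = 3: 1.20 / 1.10 = 1.09
- p1 = 20%, R = 3: 1.40 / 1.10 = 1.27
- p1 = 10%, R = 5: 1.40 / 1.20 = 1.17
- p1 = 20%, R = 4: 1.60 / 1.15 = 1.39
- p1 = 20%, R = 5: 1.80 / 1.20 = 1.50

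**Chance of a falsely significant crude result.** Take 3600 patients and 5% overall incidence (Section 10.1), and assume the technique is used in 30%. The risk without expected difficulty is 0.05 / [1 + (0.3·p1 + 0.7·p0)(R − 1)]. For p1 = 20% and R = 3 this is 0.05 / 1.19 = 0.0420, giving 0.0420 × 1.40 = 5.88% with the technique and 0.0420 × 1.10 = 4.62% without. The odds ratio is (0.0588/0.9412) / (0.0462/0.9538) = 1.29.

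| R | p1 | Spurious odds ratio | Chance of p < 0.05 |
|---|---|---|---|
| 2 | 10% | 1.05 | 0.05 |
| 3 | 10% | 1.10 | 0.08 |
| 3 | 20% | 1.29 | 0.36 |
| 3 | 30% | 1.49 | 0.70 |
| 5 | 10% | 1.18 | 0.18 |
| 5 | 20% | 1.53 | 0.77 |

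The chances use a two-sided normal approximation without continuity correction. The Yates correction planned in Section 10.2 would lower them somewhat. A larger sample does not reduce the bias.

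All these figures are for the unadjusted comparison. The documents give nothing from which to compute how much the measured covariates would remove.

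**The case against.** The case for leaving the plan alone has several parts.

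**The project is descriptive.** It is a service evaluation, Aim 2 speaks only of possible association, and no causal claim is made. Descriptive reporting does remain valid. But Section 10.2 goes further, with adjusted estimates and a significance threshold, and readers will take an adjusted estimate as informative about risk.

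**The bundle is mainly PPE.** The Protocol never lists videolaryngoscopy, stylet or flexible bronchoscope as bundle components, and the Introduction ties management partly to COVID-19 status, which is collected. This stands for PPE, where confounding by expected difficulty is weaker. It does not dispose of technique and equipment, which Aim 2 and the Introduction bring within scope.

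**The proxies do much of the work.** They do some of it, and the crude figures above should be read with that in mind.

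**Stronger readings.** A reader might infer that techniques chosen for expected difficulty are bound to look harmful. That does not follow: the composite counts poor laryngoscopic view and change of device, and a technique chosen in advance could lower either, offsetting the confounding. A reader might also infer that the outcome of unanticipated difficulty cannot be measured. Departure from the original plan is a workable definition, and it is recorded. The CRF question for it is only partly legible in the text read here, but the Section 9.1 item is clear.

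**A new tick box may be filled in with hindsight.** This is fair. Section 9.1 does not require the CRF to be completed before induction, so the wording of the item matters.

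**Conclusion.** The gap is real and confined to technique and equipment components. Their adjusted associations with the composite may be confounded by indication, the collected variables can reduce this only in part, and later analysis cannot recover what was not recorded. Under the assumed 5% versus 10% to 20% and 3- to 5-fold risk, the crude spurious risk ratio is 1.09 to 1.50. Bias after the planned adjustment would probably be smaller, and its size cannot be derived from the documents. At the low end it is negligible; at the high end it could pass for a finding. The primary incidence is unaffected. This is a change that should be made because it is cheap and must precede data collection; the gap does not undermine the main aim.

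**What to change.** Add one item to Section 9.1, the CRF and REDCap: *Difficult airway anticipated at pre-operative assessment, before induction: yes / no*. A CRF note should ask that it be taken from the documented airway assessment where there is one. Include it in the multivariable model, and report technique and equipment associations stratified by it.

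The cost is one extra tick box per patient. Some hindsight misclassification will remain where it is completed after induction, and adjusting for an answer coloured by the event could over-correct. The stratum with anticipated difficulty would also be small: under the assumptions above with p1 = 10% to 20%, 3600 × (0.3 × 0.10 + 0.7 × 0.05) = 234 to 3600 × (0.3 × 0.20 + 0.7 × 0.05) = 342 patients. Estimates within it will be imprecise.

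If the item cannot be added, state in Section 10.2 that technique and equipment associations are descriptive and subject to confounding by indication. Add a sensitivity analysis for an unmeasured confounder, for example by applying the formula above to the adjusted estimates over a stated grid of p0, p1 and R.
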